10.2.2 Evaluation of Circulating Tumor Cells (CTC)

Count of CTC

For counting CTCs are isolated by means of the CellSearch® Circulating Tumor Cell Kit (Veridex LLC, Raritan, USA).

Assessment of HER2 Status of Circulating Tumor Cells

Blood samples will be collected into CellSave tubes (Veridex Inc.). The CellSearch Epithelial Cell Test (Veridex Inc.) will be applied for CTC enrichment and enumeration. The method has been described in detail elsewhere (Riethdorf et al. 2007). In brief, CTCs are captured from peripheral blood by anti-epithelial cell adhesion molecule (EpCAM)-antibody-bearing ferrofluid and subsequently identified by cytokeratin-positivity/negativity for the leukocyte common antigen CD45 and 4',6-diamidino-2-phenylindole (DAPI) staining to ensure the integrity of the nucleus. A blood sample is considered positive when at least one CTC is present based on the prognostically relevant cut-off as previously published (Cristofanilli et al. 2004, Budd et al. 2006). HER2 expression of CTCs will be characterized within the CellSearch assay by addition of a fluorescein isothiocyanate (FITC)-labeled anti-HER2 antibody (CellSearch tumor phenotyping reagent HER2, Veridex Inc.), as described previously (Hayes et al. 2002, Meng et al. 2004, Riethdorf et al. 2010). The intensity of the HER2-specific immunofluorescence will be categorized into negative (0), weak (1+), moderate (2+), and strong (3+). CTCs are considered HER2 negative, if all measured CTCs have a moderate HER2 staining (2+) or less based on the cut-off level published by Riethdorf et al. 2010.

10.2.3 Evaluation of Quality of Life

The EORTC QLQ-C30 and EORTC QLQ-BR23 questionnaires are used (see APPENDIX V – QUALITY OF LIFE ASSESSMENTS). Data are analyzed according to the respective EORTC manuals.

11 ADVERSE EVENT REPORTING

11.1 Definitions, Collection and Recording of Adverse Events by the Investigator

An adverse event (AE) is any untoward medical occurrence in a patient administered a pharmaceutical product and which does not necessarily have a causal relationship with this treatment. An adverse event (AE) can therefore be any unfavorable and unintended sign (including an abnormal laboratory finding), symptom, or disease temporally associated with the use of a medicinal (investigational) product, whether or not related to the medicinal (investigational) product. In particular this includes new findings or changes from baseline in laboratory test results or any other safety assessments (e.g. ECGs, radiological scans, vital signs assessments) felt to be clinically significant in the medical and scientific judgment of the investigator.

During treatment period AEs are collected by the investigator at least on every visit of the patient at the study site, whether it is a scheduled study visit or not.

During the follow-up period (after conclusion of the treatment period) only adverse events are collected by the investigator which are \geq grade 3 NCI CTCAE and/or serious.

Every adverse event is followed up until it has subsided or stabilized.

On each AE the following data are raised and documented by the investigator in the respective electronic case report form:

- Diagnosis or each single symptom if diagnosis is not available,
- Date and time of onset and end of AE,
- Whether onset was after the first administration of study medication (yes/no),
- Course (continuous / intermittent, if intermittent: number of episodes),
- Whether the AE is a reportable serious adverse event (serious/ non-serious, for the definition of "reportable serious event" cf. section 1.3),
- Intensity (grade 1 to 5 according to the NCI Common Terminology Criteria for Adverse events (CTCAE) version 4.03),
- Causal relationship with investigational medicinal product (no (not related) / yes (reasonable possibility)),
- Counter-measures (none/ dose reduced/ drug withdrawn/ other drug treatment/ other measures),
- Outcome (recovered/ recovering/ not recovered/ recovered with sequelae/ fatal/ unknown),

To allow for a more appropriate evaluation of adverse events, toxicities due to previous anticancer medication which occurred before inclusion visit are also reported specifying the kind of toxicity, start date, end date / specification if ongoing, and severity according to NCI CTCAE Version 4.03.

11.2 Definitions, Collection and Expedited Recording of Serious Adverse Events by the Investigator

A serious adverse event (SAE) is any adverse event that at any dose

- Results in death
- Is life-threatening
- Requires inpatient hospitalization or prolongation of existing hospitalization (excluding hospital admissions for study drug administration, transfusional support for the purposes of decreasing hematological toxicity (e.g. GCSF), elective surgery and admissions for palliative or terminal care)
- Results in persistent or significant disability or incapacity and/or
- Is a congenital anomaly/birth defect.
- Is a medically important event or reaction:

Medical and scientific judgment should be exercised in deciding whether other situations should be considered serious such as important medical events that might not be immediately life-threatening or result in death or hospitalisation but might jeopardise the patient or might require intervention to prevent one of the other outcomes listed in the definition above. Examples of such events are intensive treatment in an emergency room or at home for allergic bronchospasm, blood dyscrasias or convulsions that do not result in hospitalization, or development of drug dependency or drug abuse. In Addition any suspected transmission of an infectious agent via a medicinal product is considered an important medical event

The investigator shall report all serious adverse events (including serious adverse reactions and suspected serious adverse reactions) to the sponsor immediately (within 24 hours) after becoming aware of them. Each serious adverse event must be documented on the electronically available "**Serious adverse events report**" form. The completed form is automatically faxed (fax no. is filed automatically in the system) to the sponsor and Alcedis GmbH. In the event that electronic reporting is not possible, paper SAE forms in the investigator's file handed out at the beginning of the study are at the doctor's disposal for notification by conventional fax.

11.3 Collection and Recording of Other Events by the Investigator

The investigator shall report misuse and abuse of an IMP, other medication errors and uses outside of what is foreseen in the protocol (irrespective if a clinical event has occurred).

SPONSOR'S STUDY OFFICE:

Universitätsklinikum Ulm
Studienzentrale
[name]
[name]
Germany

Physician: Dr. [name]; Dr. [name], Dr. [name], [name], [name], Prof. [name], Prof. [name]
Studycoordinators: [name], [name], [name]

[contact]
[contact]
Email: [contact]

Complete information on the SAE may not be available initially. Initial SAE reports should be submitted as soon as the following minimum information has been obtained:

- EudraCT Number
- Patient identification number
- The investigational medicinal product
- An AE assessed as serious
- Name and address of investigator and clinical trial center

In case of incomplete information at the time of initial SAE reporting, the initial report must be followed by further relevant information immediately after receipt. In certain cases it may be appropriate to follow-up the initial reports by several times.

Medical and scientific judgment should be exercised in deciding whether expedited reporting is appropriate in other situations such as important medical events that may not be immediately life-threatening or result in death or hospitalization but may jeopardize the patient or may require intervention to prevent one of the events listed above.

Please Note:

- An event which is part of the natural course of the disease under study (e.g. hospitalization for signs/symptoms of the disease or disease progression or death due to disease progression) does not need to be reported as a SAE even though serious criteria are met. However, if the progression of the underlying disease is greater than that which would normally be expected for the subject, or if the investigator considers that there was a causal relationship between protocol treatment or protocol design/procedures and the disease progression, then this must be reported as a SAE.
- For each serious adverse event a corresponding AE must be documented within the eCRF.

Every serious adverse event is followed up until it has subsided or stabilized.

11.4 Sponsor Responsibilities

General Remarks:

When patient data are transferred as described below they must be pseudonymous. This means instead of data allowing patient identification the unique patient identification numbers are specified only.

AE Reporting:

On request of the competent authority detailed records have to be submitted on all adverse events which have been reported by the investigators

Annual Safety Report (ASR) with Serious Adverse Reaction (SAR) Listing:

All noxious and unintended responses to a medicinal product related to any dose are to be considered as adverse drug reaction (AR). "Response to a medicinal product" means that a causal relationship between a medicinal product and an adverse event is at least a reasonable possibility, i.e. the relationship cannot be ruled out. Accordingly a Serious Adverse Reaction (SAR) is an AR which is serious according to the criteria given in section

Once a year throughout the clinical trial as well as on request, the sponsor has to provide the competent authority and the competent ethics committee with a listing of all suspected serious adverse reactions (SARs) which have occurred over this period and with a report concerning the clinical trial participant's safety (annual safety report, ASR).

SUSAR and other Safety Issue Reporting:

A Suspected Unexpected Serious Adverse Reaction (SUSAR) is a suspected adverse reaction related to an investigational medicinal product (IMP) or comparators which occurs in the clinical trial, and which is both unexpected and serious. Adverse reactions are considered unexpected if not listed in the latest version of the "Fachinformation" (German SPC).

Suspected unexpected serious adverse reactions (SUSAR) have to be reported to the competent authority and to the competent ethics committees immediately but within a maximum of fifteen days of first knowledge by the sponsor. In this case patient data are passed pseudonymous to the federal and European authority.

This also holds in case of any other issues which might require re-assessment of the risk-benefit ratio of the IMP. Such safety issues may be:

- single case reports of an expected serious adverse reactions with an unexpected outcome (e.g.: a fatal outcome),
- an increase in the rate of occurrence of an expected serious adverse reaction, which is judged to be clinically important,
- post-study SUSARs that occur after the patient has completed the clinical trial and are reported by the investigator to the sponsor,
- events relating to the conduct of the trial or the development of the investigational medicinal product likely to affect the safety of the subjects.

SUSARs which are fatal or life threatening must be reported within a time limit of 7 days. Relevant follow-up information must be provided within additional 8 days.

The sponsor also informs the investigators involved in the study immediately on any SUSARs which occur. The time limit also is 15 days. In case of fatal or life-threatening SUSARs the time limit is 7 days, further relevant information must be provided within additional 8 days.

Reporting of safety measures taken for patient protection:

Sponsor and investigator take immediate measures to protect trial participants from immediate hazard, if new or unforeseen conditions might compromise the participants' safety. In that case, the sponsor informs the competent authority and the ethics committee immediately about the measures taken and the conditions which caused their origination.

Reporting of clinical safety information to Novartis

All serious adverse events occurring in a patient who has been treated with the IMP everolimus/ribociclib of Novartis shall be reported by the sponsor to Novartis within 24 hours after becoming aware of them.

The sponsor will notify all SAEs reporting to Novartis Pharma GmbH (Abteilung Arzneimittelsicherheit; [name]; [name]; Fax-Nr.: [name]) on the appropriate report forms.

Reporting of clinical safety information to Eisai

All serious adverse events occurring in a patient who has been treated with the IMP eribulin of Eisai shall be reported by the sponsor to Eisai within 24 hours after becoming aware of them.

The sponsor will notify all SAEs reporting to Eisai GmbH (Abteilung Arzneimittelsicherheit; [name]; [name]; Fax-Nr.: [name]) on the appropriate report forms.

Reporting of clinical safety information to TEVA

All serious adverse events occurring in a patient who has been treated with the IMP Lipegfilgastrim of TEVA shall be reported by the sponsor to TEVA within 24 hours after becoming aware of them.

The sponsor will notify all SAEs reporting to TEVA GmbH (Abteilung Arzneimittelsicherheit; [name] [name], Fax-Nr.: [contact] 77) on the appropriate report forms.

12 PREGNANCY

All pregnancies that occur during the study, or within 14 days of completion of the study, are to be reported immediately to the sponsor, and the investigator must provide the sponsor with the pregnancy form. The process for reporting a pregnancy is the same as that for reporting a serious adverse event.

Any patient becoming pregnant during the study will be withdrawn. All patients who become pregnant will be monitored to the completion or termination of the pregnancy. If the pregnancy continues to term, the outcome (health of the infant up to 8 weeks of age), including spontaneous or voluntary termination, details of birth, and presence or absence of any birth defect, congenital abnormalities, or maternal and newborn complications, will be reported to the sponsor. Any complication of pregnancy will be reported as an adverse event or serious adverse event, as appropriate.

If the pregnancy does not continue to term, 1 of the following actions will be taken:

- For a spontaneous abortion, report as a serious adverse event.
- For an elective abortion due to developmental anomalies, report as a serious adverse event.
- For an elective abortion **not** due to developmental anomalies, report on the pregnancy form.

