PR	Partial Response
QOL	Quality of Life
RAD001	Everolimus
RANKL	Receptor activator of nuclear factor kappa B ligand
RECIST	Response Evaluation Criteria In Solid Tumors
SAE	Serious Adverse Event
SAR	Suspected Adverse Reaction
SD	Stable Disease
SGPT	Serum Glutamic-Pyruvic Transaminase

SPC	Summary of Product Characteristics
SUSAR	Suspected Unexpected Serious Adverse Reaction
TK	Tyrosine Kinase
TNBC	Triple negative breast cancer
TTP	Time To Progression
YOB	Year of Birth

EUDRACT-NO.: 2013-001269-18	Protocol No.: D-IV
Sponsor: Universitätsklinikum Ulm (AöR), [name], [name]	
Responsible person: [name]. [name], University Hospital Ulm	
Coordinating Investigator („Leiterin der klinischen Prüfung“ acc. to German Drug Law): [name]. [name], University Hospital Düsseldorf	
Title: DETECT IV – A prospective, multicenter, open-label, phase II study in patients with HER2-negative metastatic breast cancer and persisting HER2-negative circulating tumor cells (CTCs).	
Investigational medicinal products (IMP): DIVa: Everolimus tablets 5 mg/Ribociclib capsules 3 x 200 mg /d d 1-21 q28d or DIVb: Eribulin mesylate 1.23 mg/m² d1+8 q3w	
Indication/Clinical Trial population	

Everolimus/Ribociclib cohort: Postmenopausal female patients with hormone-receptor positive, HER2-negative metastatic breast cancer with only HER2-negative circulating tumor cells (CTCs) and indication for standard endocrine therapy.
	

Eribulin cohort: Patients with hormone-receptor positive, HER2-negative metastatic breast cancer and indication to chemotherapy or patients with triple-negative metastatic breast cancer, both with only HER2-negative circulating tumor cells (CTCs).
	

Clinical Trial Design

A prospective, multicenter, open-label, phase II study.

[figure not shown]

Figure 1: Screening and Design of DETECT IV

Planned duration of the entire study

The study starts when the necessary approval has been given by the competent authority (BfArM). Furthermore the competent ethics committee must have given a favorable opinion on study conduct before the first patient is included.

The trial is terminated after the last patient has either died or completed the 24-months follow-up period.

The maximum study duration is 72 months and 3 weeks.

Planned duration of individual study participation

The individual study participation begins with the screening visit and ends when the patient has either died or completed the 24-months follow-up period.

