A study evaluated the PK of eribulin in patients with mild (Child-Pugh A; $n=7$) and moderate (Child-Pugh B; $n=4$) hepatic impairment due to liver metastases. Compared to patients with normal hepatic function ($n=6$), eribulin exposure increased 1.8-fold and 3-fold in patients with mild and moderate hepatic impairment, respectively. Administration of eribulin at a dose of 0.97 mg/m^2 to patients with mild hepatic impairment and 0.62 mg/m^2 to patients with moderate hepatic impairment resulted in a somewhat higher exposure than after a dose of 1.23 mg/m^2 to patients with normal hepatic function. Eribulin was not studied in patients with severe hepatic impairment (Child-Pugh C). There is no study in patients with hepatic impairment due to cirrhosis.

Renal impairment

A study in patients with different degrees of impaired renal function showed that the exposure of eribulin in patients with moderate renal function (creatinine clearance ≥ 40 to 59 ml/min , $n=6$) was similar to patients with normal renal function while the exposure in patients with severe impairment was increased by 75% (creatinine clearance $< 40 \text{ ml/min}$, $n=4$).

Elderly population

In studies of 1,222 patients treated with eribulin, 244 patients (20.0%) were $> 65 - 75$ years of age and 66 patients (5.4%) were > 75 years of age. Among the 827 of these patients who received the recommended dose of eribulin in the Phase 2/3 breast cancer studies, 121 patients (14.6%) were $> 65 - 75$ years of age and 17 patients (2.1%) were > 75 years of age. The safety profile of eribulin in elderly patients (> 65 years of age) was similar to that of patients ≤ 65 years of age. No dose adjustments are recommended for the elderly population.

Pregnancy

There are no data from the use of eribulin in pregnant women. Eribulin is embryotoxic, foetotoxic and teratogenic in rats. Eribulin should not be used during pregnancy and women of childbearing potential must be advised to avoid becoming pregnant whilst they are receiving eribulin by using effective contraception during and up to 3 months after treatment.

For the most up to date safety information, please refer to the most current edition of the Investigator's Brochure.

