
 • Any endocrine therapy in the history is allowed. • Disease progression following prior treatment with endocrine therapy (endocrine therapy does not have to be the last therapy before inclusion in the trial). • Postmenopausal women. The investigator must confirm postmenopausal status Postmenopausal status is defined either by 
 - Age \geq 55 years and one year or more of amenorrhea - Age $<$ 55 years and one year or more of amenorrhea and postmenopausal levels of FSH and LH - Prior hysterectomy and has postmenopausal levels of FSH and LH - Surgical menopause with bilateral oophorectomy 
Everolimus cohort:
 
 • Cholesterol \leq 2.0 \times ULN 
Ribociclib cohort:
 
 • Standard 12-lead ECG values assessed by the local laboratory: 
 - QTcF interval at screening $<$ 450 msec (using Fridericia's correction) - Resting heart rate 50-90 bpm • INR \leq 1,5 (ribociclib cohort) • Patients must have the following laboratory values within normal limits or corrected to within normal limits with supplements before the first dose of study medication: 
 -Sodium -Potassium -Total calcium 	
 - Negative pregnancy test (minimum sensitivity 25IU/L or equivalent units of HCG) within 7 days prior to recruitment - Contraception by means of a reliable method (i.e. non-hormonal contraception, IUD, a double barrier method, vasectomy of the sexual partner, complete sexual abstinence). Patient must consent in maintaining such contraception until 3 months after completion of study treatment
---	---

Ineligibility Criteria

Patients who fulfill any of the following criteria are not eligible for recruitment:

Exclusion Criteria	
In General for both study cohorts	
Treatment with other investigational agents of any type or anticancer therapy during the trial, within 2 weeks prior to the start of treatment.	
1. Adverse events due to prior anticancer therapy which are > Grade 1 (NCI CTCAE) and therapeutically relevant at time of treatment start.	
2. Known HIV infection.	

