8.4.1.9 Instructions for use of study drug

Patients will receive cycles of 1.23 mg/m² eribulin on days 1 and 8 of a 21-day cycle for 12 months or until disease progression, unacceptable toxic effects, patient or physician request for discontinuation, or serious protocol non-compliance. Eribulin as the ready to use solution is administered intravenously over 2 to 5 minutes. In the EU the recommended dose refers to the base of the active substance (eribulin). Calculation of the individual dose to be administered to a patient must be based on the strength of the ready to use solution that contains 0.44 mg/ml eribulin.

Monitoring of complete blood counts should be performed on all patients prior to each dose of eribulin. Treatment with eribulin should only be initiated in patients with ANC values \geq 1500/ μ l and platelets $>$ 100000/ μ l. The dose reduction recommendations shown below are also shown as the dose of eribulin to be administered based on the strength of the ready to use solution.

Method of administration

The dose may be diluted in up to 100 ml of sodium chloride 9 mg/ml (0.9%) solution for injection. It should not be diluted in glucose 5% infusion solution. Good peripheral venous access, or a patent central line, should be ensured prior to administration. There is no evidence that eribulin mesilate is a vesicant or an irritant. In the event of extravasation, treatment should be symptomatic.

Women of childbearing potential must be advised to avoid becoming pregnant during and up to 3 months after treatment.

All dosages prescribed and dispensed to the patient and all dose changes during the study must be recorded on the Dosage Administration Record CRF.

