13.1.3 Therapy after End of Protocol Treatment

Therapy during the follow-up period will be according to current guidelines and is at the discretion of the investigator, regardless of whether the protocol treatment could be completed as planned or had to be discontinued prematurely). The treatment with everolimus/ribociclib can be extended in case of missing progress. The drug will be supplied by Novartis on study terms for the duration of the individual study participation (including 2-year-period of follow-up assessments). In case of clinical benefit the treatment with eribulin can be continued until progression of disease; the study drug will be (within the off-label use) supplied by Eisai as well.

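### Pregnancy reporting closes 14 days after an undefined study completion, so eribulin patients whose participation ends at or near the last dose are not covered for the protocol's own 3-month pregnancy-avoidance period

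*Protocol*

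**What the plan says.** Section 12 sets the reporting duty: "All pregnancies that occur during the study, or within 14 days of completion of the study, are to be reported immediately to the sponsor". It sends these reports through the serious-adverse-event process and asks for follow-up of the pregnancy and of the infant to 8 weeks of age. It does not say whether completion refers to the individual patient or to the whole trial.

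For eribulin, section 3.4.6 states the reason for concern, "Eribulin is embryotoxic, foetotoxic and teratogenic in rats", notes that there are no data in pregnant women, and advises "using effective contraception during and up to 3 months after treatment". Section 5.1 makes this a condition of entry: "Patient must consent in maintaining such contraception until 3 months after completion of study treatment". Section 8.4.1.9 repeats it: "Women of childbearing potential must be advised to avoid becoming pregnant during and up to 3 months after treatment".

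On when participation ends, the synopsis says that it "ends when the patient has either died or completed the 24-months follow-up period". The opening of section 4.3 adds disease progression as an end point, although the follow-up entry in the same section runs to death or 24 months. Section 8.4.2 moves a patient who permanently stops eribulin into the 2-year follow-up. Sections 8.4.2.1 and 8.6.4 say that a patient with an interruption of more than 4 weeks is discontinued from the study.

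Eribulin may also be given beyond the 12-month treatment period. Section 13.1.3 says: "In case of clinical benefit the treatment with eribulin can be continued until progression of disease".

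**The concern.** The reporting window is counted from the study and the pregnancy-avoidance period from treatment. For most patients the study outlasts treatment by far, and the difference does no harm. It matters where the two end together: early termination of participation (13.2), a stop of the whole study (13.4), progression if the opening of section 4.3 is taken literally, or eribulin continued to the end of follow-up. In those patients the duty to report lapses well before the period in which the protocol itself asks women not to conceive.

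At stake is safety information. With rat teratogenicity and no human data stated in section 3.4.6, each exposed pregnancy and its outcome is informative, and section 12 exists to collect them. Only the eribulin cohort is concerned, because the everolimus/ribociclib cohort is postmenopausal.

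**Working it through.** The plan gives no figure to reproduce. The check is calendar arithmetic, counting from the last eribulin dose as day 0.

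Inputs:
- Pregnancy-avoidance period: 3 months (3.4.6, 5.1, 8.4.1.9), which is 89 to 92 days depending on the calendar, about 91.
- Reporting: to the end of participation plus 14 days (section 12, reading completion as the individual patient's).
- Follow-up: 24 months (synopsis), at least 730 days.
- Conclusion Visit: 4 weeks after the last application (4.3), 28 days.

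Formula: uncovered days = 3 months − (day participation ends + 14), not below 0.

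| Route | Report required to day | Uncovered days |
|---|---|---|
| Stops eribulin, completes 24-month follow-up | 730 + 14 = 744 | 0 |
| Leaves at last dose, or on eribulin to the last day of participation | 0 + 14 = 14 | 89 − 14 = 75 to 92 − 14 = 78 |
| Leaves at the 4-week visit, or is taken off the study just after a 4-week interruption | 28 + 14 = 42 | 89 − 42 = 47 to 92 − 42 = 50 |

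With 91 days, the last two rows are 77/91 = 85% and 49/91 = 54% of the period.

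Do other rules close the gap? Section 13.1.1 ends adverse-event collection 28 days after the last dose, which would still leave 89 − 28 = 61 to 92 − 28 = 64 days. That sentence also sits badly with sections 9.2 and 11.1, which collect serious and grade 3 or higher events through follow-up. Section 11.4 deals with post-study SUSARs that an investigator chooses to report; it creates no duty to report a pregnancy.

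How many women? The protocol does not say, so this rests on assumptions:
- Early leavers: 120 enrolled × the 10% loss to follow-up assumed in section 15.3 = 12. If 25% are not postmenopausal (the complement of the 75% assumed for hormone-receptor-positive patients), 12 × 0.25 = 3.
- Ceiling: 120 × 0.25 = 30, reached only if every such woman in the cohort left at or soon after her last dose.
- Still on eribulin at month 36 (12 + 24): with the assumed median PFS of 3.7 months and an exponential curve (an assumption), 2^(−36/3.7) ≈ 0.0012; × 120 ≈ 0.14 patients; × 0.25 ≈ 0.04 women.

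The 25% is itself rough. About 270 of the 390 patients expected to be eligible for this cohort are triple-negative, and not being postmenopausal is not the same as being of childbearing potential.

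**The case against.** The strongest reply is that the usual route has no gap. The 14 days run from study completion, not from the last dose, and section 8.4.2 places a patient who stops eribulin in follow-up, with contacts at 2 to 4 weeks and then at least every 3 months (9.2). This stands. A reader might infer from section 12 that reporting stops 14 days after the last dose for everyone, or that 85% of the period is generally uncovered; the protocol supports neither. The 85% is the extreme case of leaving on the day of the last dose.

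Second, sections 4.3 and 8.6.2 define the end of the study for the trial as a whole. If section 12 means that, early leavers stay inside the window until the trial closes, and only women dosed near its end are exposed. This also stands as a possible reading. But section 12 does not say which is meant, and a patient on eribulin at the very end is uncovered on either reading.

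Third, the 4-week-interruption route is uncertain. Section 13.1.1 describes study discontinuation as withdrawal from study drug, which under section 8.4.2 would lead into follow-up and leave no gap. The passages disagree and should not carry the argument alone.

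Fourth, a voluntary report remains possible, and a congenital anomaly is a seriousness criterion in section 11.2. So the finding is that no report is required, not that none would arrive.

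Finally, new text cannot bring data from a woman who has withdrawn consent. That limits the benefit of the fix without removing it.

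**Conclusion.** The mismatch is real but narrow. Section 12 and the 3-month period in sections 3.4.6, 5.1 and 8.4.1.9 do not fit together for eribulin patients of childbearing potential whose participation ends at or soon after the last dose. If completion is read patient by patient, the uncovered time is 75 to 78 days for a woman leaving at her last dose and about 49 days for one leaving at a 4-week visit. The gap also exists for a patient on eribulin to the end of follow-up, but that group is almost empty on the protocol's own PFS assumption.

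The number exposed is probably a few. A reader might infer about 30 from the cohort size, but that counts every woman assumed not to be postmenopausal, including those whom follow-up covers fully. These are women exposed to the gap, not expected pregnancies. The primary analysis and all efficacy endpoints are untouched. The correction is worth making because it is cheap and the information is scarce.

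**What to change.** Reconcile section 12 with sections 3.4.6, 5.1 and 8.4.1.9. Keep the present window and anchor it also to the last eribulin dose, so that reporting runs at least as long as the protocol's own contraception period, whichever ends later, including after premature termination under sections 13.2 and 13.4. On every route the uncovered interval then becomes 0 days. This concerns reporting only and leaves dosing and the contraception rule as they are.

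In the same edit:
- define in section 12 whether completion means the patient's participation or the whole trial;
- reconcile the synopsis with section 4.3 on whether participation ends at progression;
- reconcile section 8.4.2 with sections 8.4.2.1 and 8.6.4 on whether a long interruption leads to follow-up or out of the study.

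The cost is a few sentences in the protocol and the patient information, with the existing pregnancy form. The downside is some contact after withdrawal, limited where consent has been withdrawn.
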